#### ***Removal of Subjects Based on Device Performance***

Subjects will be withdrawn from the study if the adhesive does not adhere appropriately at the time of application as assessed by the investigator and the event will be reported as device deficiency.

#### ***Pregnancy***

Subjects will be instructed that known or suspected pregnancy occurring during the study, in subjects or female partners of male subjects, should be confirmed and reported to the investigator. The investigator should also be notified of pregnancy occurring during the study but confirmed after completion of the study. In the event that a subject is subsequently found to be pregnant after inclusion in the study, the pregnancy will be followed to term and the status of mother and child will be reported to the sponsor after delivery.

Full details will be recorded on the withdrawal page of the eCRF and a pregnancy report will be completed.

### **7.4 Investigational Medical Device**

#### **7.4.1 Investigational Medical Device Applied**

MAR-CUTIS is a polyurethane-based skin adhesive. At the time of use, the 2 components in the syringe are mixed in the mixing cannula. Complete hardening occurs about 5 minutes after application to the skin. The adhesive result can be corrected in the first 30 seconds. MAR-CUTIS is distributed sterile and is intended for single use. The product is used for topical closure of incisions and surgical wounds, replacing the last dermal suture line. It is not intended for intra-abdominal use and/or as a substitute for subcutaneous sutures. It should not be used after the expiration date and/or if the sterile packaging has been opened or damaged.

Dermabond Advanced is a topical skin adhesive used to hold closed easily approximated skin edges of wounds from surgical incisions, including incisions from minimally invasive surgery, and simple, thoroughly cleansed, trauma-induced lacerations.

#### **7.4.2 Identity of Investigational Medical Device**

The prepolymer component of MAR-CUTIS is made with hexamethylene diisocyanate, benzoyl chloride, and trifunctional polyol with primarily short alkylene oxide units. The curing agent is composed of diethyl maleate, 1,5-diamino-2-methylpentane, and polyethylene glycol 200. MAR-CUTIS should be stored at room temperature (15 to 25°C) and should be protected from moisture and humidity.

The active ingredient in Dermabond Advanced is 2-octyl cyanoacrylate. The recommended storage conditions are below 30°C (86°F), and away from moisture, direct heat, and direct light.

---

### 7.4.3 Manufacturing, Packaging, and Labeling

Manufacturing, labeling, packaging, and shipment of MAR-CUTIS will be performed by Syneos Health. All manufacturing, packaging, and labeling operations will be performed according to Good Manufacturing Practice for Medicinal Products and the relevant regulatory requirements. Details of packaging and labeling will be on file in the trial master file.

Dermabond Advanced adhesive is supplied sterile, in a prefilled, single-use applicator. The pen-style applicator consists of a crushable ampoule contained within a plastic applicator. The applicator contains the liquid adhesive. The applicator is supplied in a blister package to maintain the sterility of the device until opened or damaged. Dermabond Advanced adhesive is available in boxes of 6 or 12 applicators.

### 7.4.4 Method of Assigning Subjects to Treatment Groups

Subjects (ie, the unique subject identifier [ID] consisting of center ID and subject ID) will be randomly allocated to treatment according to a randomization scheme designed using the covariate-adjusted dynamic allocation method as implemented in Balance (Medidata, 2015). The algorithm combines complete randomness with a minimization method (Pocock and Simon, 1975), not only looking at marginal balances, but also considering the treatment balances overall and within individual strata, to ensure a balanced treatment allocation. Based on the expected clinical relevance of the explanatory variables for incision and laceration closure, the algorithm is implemented by assigning a different weight to the stratification factors to be included in the trial and minimize unbalances (ie, wound type having more importance than the other 2 factors, and age group having more importance than skin type). Further details regarding the parameters used to implement the randomization in balance are documented in the form “Balance Study Configuration Requirements”.

The incision/laceration will be prepared for closure as per the standard of care at a treating hospital. The investigator will assess the need and perform closure of deep tissue layers as necessary before proceeding with the randomization and subsequently with the closure of the last (dermal) layer with the IMD.

Eligible subjects will be randomized 2:1 to MAR-CUTIS or Dermabond Advanced.

The study will include 3 levels of stratification as randomization factors:

- By wound type (lacerations and incisions).
- By skin type according to the Fitzpatrick classification (types I to III versus types IV to VI).
- By age group (aged 2 to 21 years and  $\geq 22$  years).

The primary efficacy analysis will consider the stratification factors as explanatory variables in the model. Additionally, center will be considered as a further randomization factor as recommended by International Council for Harmonisation (ICH) E9.

### 7.4.5 Application in the Study

Detailed instruction and a training video on the application of MAR-CUTIS will be provided to each investigational site. MAR-CUTIS will be applied in one 1 to 2 mm thick layer, ensuring that at least 1 cm of the glue is applied over the length of the wound on each side.

---

The amount of the glue applied will be calculated such that one 5-mL syringe covers approximately 8 cm of wound length (giving a total of 10 cm per syringe). For wounds >8 cm, 2 syringes will be required. The wound will be held for approximately 30 seconds to allow for initial polymerization. Only for the pediatric population, the maximum number of syringes per day is limited based on the body weight as shown in the table below:

Body Weight	Number of MAR-CUTIS Syringes
10 to <15 kg	Maximum of 1 syringe
15 kg and above	Maximum of 2 syringes

Detailed instruction and a training video on Dermabond Advanced application will also be provided to each investigational site. Use of Dermabond Advanced will be according to Instructions for Use (Section 15.2). Dermabond Advanced will be applied in one continuous layer onto a dry wound through painting motions, taking care not to apply adhesive between the wound edges. Applying a second layer is not required or recommended. If a second layer of Dermabond Advanced is applied or if large droplets of liquid are not spread thinly, the subject may experience an increased sensation of heat or discomfort. The wound will be held for 60 seconds to allow for complete polymerization.

#### **7.4.6 Timing of Application for Each Subject**

The IMD will be applied only on Day 0 as instructed in Section 7.4.5.

#### **7.4.7 Blinding**

Blinding is not applicable as this is an open-label study.

In the given context, a blinding of investigators, site staff, and subjects is not feasible due to visual differences between the two adhesives, and therefore the possibility to distinguish both products. The assessment of the dehiscence and other endpoints might be prone to bias given the open-label trial design. To minimize the potential bias, sites will provide adequate training to all device users and further site staff involved in the trial in cooperation with the Sponsor.

#### **7.4.8 Prior and Concomitant Therapy**

Medication taken within the two weeks before screening will be documented in the eCRF. Allowed medications include those not listed in Section 7.4.8.1. Intraoperative anesthesia is not considered concomitant medication and does not require capturing in the eCRF.

##### **7.4.8.1 Prohibited Medication/Therapy**

Prohibited medications are chronic, pre-operative steroids, immunosuppressants, chemotherapy, and anticoagulants; only chronic anti-platelet therapies like acetylsalicylic acid (ASA) and clopidogrel are accepted. Chronic is to be interpreted as long term or “for more than acute treatment”. Pre-operative standard of care, like a single dose of an anticoagulant, for the aforementioned treatments is allowed along with standard of care post-operative anticoagulant and chemotherapy regimen including application of steroids and immunosuppressants.

---

#### **7.4.8.2 Rescue Medication**

Not applicable.

#### **7.4.9 Treatment Compliance**

The IMD will only be applied on Day 0 by the investigator. The timing of the glue detachment will be noted and recorded in the eCRF (day of application). Early glue removal and reason for removal will also be recorded in the eCRF.

#### **7.4.10 Device Deficiencies Reporting**

Device deficiencies (complaints and malfunctions) will be recorded in the subject diary. The investigator shall record all observed device deficiencies together with an assessment in the eCRF. If the device deficiency leads to an SAE, an SAE form must also be completed (see Section 9.3.2).

The Sponsor will ensure that the device can be inspected for defects in the event of procedural complications and root cause analysis will be done.

### **8 TIMING OF STUDY PROCEDURES**

Subjects/legal guardians will provide written informed consent/assent before any study-related procedures are performed. The planned study assessments are in Section 7.1.2.

#### **8.1 Treatment**

##### **8.1.1 Screening Visit (Day -21 to 0)**

- Review and sign informed consent/assent form.
- Assess for eligibility (against the inclusion and exclusion criteria).
- Collect medical and surgical history (including diabetes mellitus, chronic obstructive pulmonary disease, hematological and vascular disorders, disorders of immune system, congestive heart failure, cardiovascular disease, smoking, and alcohol abuse).
- Record demographic data, such as ethnic origin, race, age, and sex.
- Record prior and concomitant medication (including steroids, immunosuppressants, chemotherapy, anticoagulants, and antibiotics. Excluding related to intraoperative anesthesia).
- Record adverse events (if applicable and if not recorded as medical history).

##### **8.1.2 Baseline Visit (Day 0)**

Screening and baseline can occur on the same day. The following procedures will be performed at the Baseline Visit:

- Reassess for eligibility against the inclusion and exclusion criteria if baseline is not on the same day as screening.
- Record concomitant medication (Excluding related to intraoperative anesthesia).

- 
- Record adverse events.
  - Record of incidents and device performance, device-related complaints
  - Perform a urine beta-human chorionic gonadotropin ( $\beta$ -HCG) pregnancy test (in all female subjects of childbearing potential [post-menarchal and pre-menopausal]).
  - Issue a subject diary.
  - Subject-related questionnaire completed by investigator.
  - Evaluation of incision/laceration (incidence and grading).

When all the baseline procedures have been performed, subjects will be randomized (the 3 stratification factors of age group, wound type, and skin type will be recorded). All wounds, including those that require debridement and/or deep suturing, will be prepared for closure as per the standard of care at a treating hospital. The investigator will assess the need and perform closure of deep tissue layers as necessary before proceeding with the closure of the last (dermal) layer with the IMD. Once the IMD has been applied to the wound, the investigator will complete the specified portion of the subject-related questionnaire.

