### Study Duration:

The overall study duration for each subject is up to 4 months:

- Day -21 to Day 0: screening, presurgical examination.
- Day 0: presurgical examination, surgery, final eligibility, allocation to treatment group, treatment.
- Follow-up visits: Day 1, Day 10, Month 1, and Month 3 or Early Discontinuation.

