### Screening and Randomization

Only one incision/laceration will be treated with the IMD. If a subject has more than one incision/laceration, the target wound will be the one with the greatest length (ie, the longest) that meets the study entry criteria. If the length of 2 or more wounds is equal, the investigator can choose either of them to be the target wound.

The incision/laceration will be prepared for closure as per the standard of care at a treating hospital. The investigator will assess the need and perform closure of deep tissue layers as necessary before proceeding with the closure of the last (dermal) layer with the IMD.

All lacerations will first be assessed for the need of deep suturing and/or debridement; this information will be recorded in the electronic case report form (eCRF). Wounds that require debridement and/or deep suturing will be treated according to the local practice of the investigator and only at the time of skin closure will the lacerations be randomized into 1 of the 2 study treatment arms. Wounds that do not require deep suturing and/or debridement will be randomized immediately.

Re-screening is not allowed in the study.

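### Protocol 8.1.2 reads as randomising before wound preparation and deep closure, while 7.4.4, SAP 5.3 and the synopsis place randomisation after them; 8.1.2 should be reconciled.

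*Protocol*

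**What the plan says.** Five places describe when allocation happens on Day 0.

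- **Protocol 8.1.2 (Baseline Visit).** After a list of procedures: "When all the baseline procedures have been performed, subjects will be randomized". The text then continues "All wounds, including those that require debridement and/or deep suturing, will be prepared for closure as per the standard of care at a treating hospital", and has the investigator "perform closure of deep tissue layers as necessary before proceeding with the closure of the last (dermal) layer with the IMD". Randomisation is not mentioned between deep and dermal closure.
- **Protocol 7.4.4 (Method of Assigning Subjects).** A nearly identical sentence, with randomisation inserted: the investigator is to "perform closure of deep tissue layers as necessary before proceeding with the randomization and subsequently with the closure of the last (dermal) layer".
- **SAP 5.3.** The same order as 7.4.4. The change table in SAP 7.1 says text was added there to clarify how the subject is prepared before randomisation.
- **Protocol synopsis, Study Duration.** "Day 0: presurgical examination, surgery, final eligibility, allocation to treatment group, treatment".
- **Protocol 7.2.1, Screening and Randomization.** For lacerations that need debridement or deep suturing, "only at the time of skin closure will the lacerations be randomized into 1 of the 2 study treatment arms". For the rest, "Wounds that do not require deep suturing and/or debridement will be randomized immediately".

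**The concern.** The trial is open-label. Protocol 7.4.7 accepts that dehiscence assessment may be biased and offers training as the mitigation. Allocating after deep closure is the only structural protection before skin closure, because it keeps the operator unaware of the arm while the deep layers are sutured. Protocol section 5 (Introduction) names suturing technique and suture material among the risk factors for dehiscence, so this step can bear on the primary endpoint.

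Eligibility is also affected. Exclusion criterion 8 concerns the thickness of the sutures required, which may not be settled until deep closure is planned or done. Section 8.1.2 asks for eligibility to be reassessed only when baseline and screening fall on different days. A subject screened and treated on the same day therefore has no recheck in that section, although the schedule in 7.1.2 marks an eligibility check on both occasions and the synopsis puts final eligibility before allocation.

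**Working it through.** This is a comparison of texts. The order each place gives is:

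| Place | Order | Applies to | How it is stated |
|---|---|---|---|
| Protocol 8.1.2 | listed procedures, randomise, prepare, deep closure, adhesive | all wounds | implied by the trigger and sentence sequence |
| Protocol 7.4.4 | prepare, deep closure, randomise, adhesive | all wounds | explicit |
| SAP 5.3 | as 7.4.4 | all wounds | explicit |
| Synopsis | surgery, final eligibility, allocation, treatment | all subjects | ordered list |
| Protocol 7.2.1 | deep suturing or debridement, randomise at skin closure | lacerations needing either | explicit |

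**Step 1: does 8.1.2 conflict?** Its trigger for randomisation is completion of a list without wound preparation or deep closure. Those steps follow in the future tense. The natural reading is randomise first. The parallel sentence in 7.4.4 differs by the very words that place randomisation between the two closures.

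**Step 2: which text is the outlier?** For incisions, 85% of subjects in the sample-size assumption, the contrary text is 7.4.4, SAP 5.3 and the synopsis. Section 7.2.1 adds support only for lacerations needing debridement or deep suturing. For incisions it requires deep closure before the dermal layer and does not mention randomisation. Section 8.1.2 stands alone.

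**Step 3: can the effect be sized?** No. The documents give neither the proportion of wounds needing deep closure nor any effect of knowing the arm. Changing the order does not alter the planned power. That figure does reproduce: exact enumeration of the unadjusted Farrington-Manning test (126 v 63, 3.05% v 0.85%, margin 8 points, one-sided 0.05) gives 85.8% against the stated 85%.

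**Step 4: illustration only.** The same test shows how few events decide the result. The statistic is z = (x/126 − y/63 − 0.08)/SE, where SE uses the two rates estimated under a difference of exactly 0.08. With y = 0, x = 5 gives p = 0.048 (pass) and x = 6 gives p = 0.090 (fail).

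Now take a true rate exactly at the margin, 0.85% + 8 = 8.85% for MAR-CUTIS, and suppose arm-aware closure averts some MAR-CUTIS dehiscences and no Dermabond ones:

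| Assumed effect on MAR-CUTIS | Chance of declaring noninferiority |
|---|---|
| none | 5.1% |
| 2% relative reduction | 5.8% |
| 5% relative reduction | 7.0% |
| one event fewer in every trial | 9.9% |

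The last row is a reduction of about 9%, since 126 × 0.0885 = 11.2 expected events and 1/11.2 = 0.09. None of these effects comes from the documents, and the direction is assumed too. The SAP's own test works on model-adjusted rates, which this does not reproduce.

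**The case against.** The strongest reply is that the design is already settled. The dedicated allocation section and the SAP give the protective order explicitly, and the SAP records that this was clarified on purpose. Section 8.1.2 is also not strictly chronological. Its list includes device performance and a questionnaire about applying the glue, neither of which can be completed before application, and the same section later has the questionnaire's relevant part filled in after application. It contains no explicit instruction to randomise and then close the deep layers. What it does say, that deep closure precedes dermal closure, is compatible with 7.4.4. A site reading the whole protocol would find the explicit rule.

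Most of this stands. It means the conflict is one of implied against explicit order, and that the sponsor's intention is not in doubt. It does not make the texts agree: 8.1.2 is the section headed for the Day 0 visit, and a reader who relies on it alone is pointed to the wrong sequence.

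Three stronger readings are tempting and not supported:

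- A reader might infer that the false-positive rate rises from 5.1% to 9.9%. That figure assumes one averted MAR-CUTIS event in every trial. It does not measure the effect of randomisation order.
- A reader might infer that 8.1.2 creates post-randomisation exclusions. No text provides for removing a randomised subject over suture thickness. A subject allocated but never treated would lack the post-treatment assessment that the Full Analysis Set requires, but nothing shows that this will happen.
- A reader might infer that 7.2.1 as a whole contradicts 8.1.2. Its explicit rule is limited to the lacerations described above, and wounds needing neither procedure are randomised at once.

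**Conclusion.** The inconsistency is real and should be corrected. Section 8.1.2 reads as placing randomisation before wound preparation and deep closure; the allocation section, the SAP and the synopsis place it after. The consequence is a possible, unquantified bias in dehiscence, limited to wounds that have deep closure at sites that follow 8.1.2 literally. That rests on two assumptions: that some sites would take 8.1.2 as the working sequence, and that knowing the arm could change how deep layers are closed. The documents make the second plausible by naming suturing technique and material as risk factors, but they show no effect. Importance is moderate: most of the text is already right and the correction is nearly free.

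**What to change.** Rewrite the closing paragraph of protocol 8.1.2 to match 7.4.4 and SAP 5.3, in this order:

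1. Wound preparation and any deep closure.
2. Confirmation of final eligibility for every subject, including those screened the same day, and covering exclusion criterion 8.
3. Randomisation.
4. Skin closure with the study adhesive.

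In the same edit, the list items that can only be completed after application should be moved below the application step, so that the list no longer serves as a misleading trigger for randomisation.

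Recording the times of deep closure and of randomisation in the eCRF is an optional audit aid. It would let the order be checked but is not needed to resolve the conflict.

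The cost is one paragraph, plus two time fields if the option is taken. Sample size, alpha, margin, visits and the analysis are unchanged.

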## 8.2 Follow-up Period

Subjects treated for lacerations may not be able to attend the Day 1 visit since they are usually not hospitalized. In this case, all attempts should be made to obtain information on potential dehiscence and AEs by phone. The reason for non-attendance should also be reported.

In case a subject is not able to attend the Day 10 visit, a telephone call can be done to capture the primary endpoint variables information. However, this is only allowed for exceptional cases and the reason for non-attendance and potential dehiscence and AEs should be recorded.

### 8.2.1 Day 1

The following procedures will be performed at Day 1:

- Record concomitant medication.
- Record AEs.
- Record of incidents and device performance, device-related complaints.
- Evaluation of dehiscence (incidence and grading).

### 8.2.2 Day 10 and Month 1

The product-related questionnaire will be completed by the investigator only once per site when the last subject randomized at the site completes the Month 1 visit.

The following procedures will be performed at both Day 10 and Month 1:

- Record concomitant medication
- Record AEs
- Record of incidents and device performance, device-related complaints

- 
- Evaluation of dehiscence (incidence and grading)
  - Evaluation of wound infection, if an infection occurred (incidence and criteria score)
  - Modified Hollander Cosmesis Scale (mHCS) completed by investigator
  - Subject-completed satisfaction questionnaire

Additional procedures performed at Month 1 include:

- Patient and Observer Scar Assessment Scale (POSAS), completed by subject and investigator
- Subject-related questionnaire completed by investigator
- Collect subject diary

